2.2.1 Clinical Data to Date

Tranexamic acid is a synthetic derivative of the amino acid lysine. Its mechanism of action is via inhibition of fibrinolysis by blocking the lysine binding site on plasminogen. It acts as a competitive inhibitor of conversion of plasminogen to plasmin and at higher concentrations a non-competitive inhibitor of plasmin.

Thrombin is a serine protease coagulant that both converts soluble fibrinogen into insoluble fibrin strands and activates factor XIII to catalyze covalent crosslinking of these strands, thereby forming a stable fibrin clot. It also promotes platelet aggregation at the site of vascular injury, via the activation of specific protease-activated receptors. Thus, exogenous topical thrombin directly activates the terminal stages of blood clot formation at the site of application.

Bupivacaine is an amino-amide local anesthetic. Onset of action is 1-17 min. Duration of action (route and dose-dependent) 2-9 hr. Half life: neonates 8.1 hours, adults: 2.7 hours. Time to peak plasma concentration (for peripheral, epidural, or caudal block): 30-45 min. Protein binding: about 95%. Metabolism: hepatic. Excretion: renal (6% unchanged).

Lidocaine is an amino-amide local anesthetic. Onset of action is 2-4 min. Duration of action (route and dose-dependent) 2 - 3.5 hr. Half life: 1.5-2 hr. Protein binding: 60-80%. Metabolism: hepatic. Excretion: renal.

Previous work by our group showed that the addition of topical thrombin to local anesthetic at the end of elective hand surgery provides for sustained postoperative pain control. Patients in that study who received thrombin and local anesthetic before wound closure had lower pain levels and were discharged from the PACU sooner than those who received local anesthetic alone. We hypothesize that the addition of a topical antifibrinolytic agent such as tranexamic acid with thrombin and local anesthetic at the end of elective hand surgery will provide even greater pain relief through the formation of a stable clot that prolongs the effect of local anesthesia. We hypothesize we will see even lower pain scores and lower number of pain pills and shorter PACU times in the postoperative period in the groups with a tranexamic acid + thrombin + local anesthetic than the groups with just thrombin + local anesthetic.

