3.1 Primary Objective

The primary objective of this study is to evaluate the effectiveness of topical antifibrinolytics, thrombin and local anesthetics on postoperative pain control in patients undergoing elective hand surgery. We want to determine the efficacy of this treatment over treatment with thrombin and local anesthetics and just local anesthetics alone to the same population of patients.

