5.6 Total Number of Participants and Sites

Patients will be recruited from NYU Langone Health and from Bellevue Hospital Center.

Recruitment will end when approximately 40 participants are enrolled. It is expected that approximately 40 participants will be enrolled in order to produce 40 evaluable participants.

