10.1 Statistical and Analytical Plans (SAP)

10.1.1 General Approach

Each arm of this randomized, single-blinded, placebo-controlled study will have a minimum of 10 patients. There will be a minimum of 40 patients in the study. Patients will be randomized using Microsoft Excel.

Simple randomization will be used to determine the treatment arm. In order for us to power our study based on a previous similar study at NYU for topical application (Haddock et al., Thrombin and Topical Local Anesthetic for Postoperative Pain Management), we will need 10 patients for each individual treatment arm to detect any difference in the outcome.

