10.1.2 Analysis of the Primary Efficacy Endpoint(s)

Data will be expressed either as a mean (SD) or median and interquartile range (IQR). To evaluate PACU time as a function of each group, a one way analysis of variance test followed by a Tukey-Kramer post hoc test will be performed. To assess the number of pain pills need as a function of each group, a Kruskal-Wallis test followed by a Dunn post hoc analysis will be performed. To compare pain levels between the treatment arms, pain scores on a scale of 1 (lowest aka no pain) to 10 (highest pain experienced in life) will be collected daily via a patient log. They will be analyzed as a change from baseline (preoperative) pain levels and analyzed used a series of two proportion z tests with a family error rate equal to 0.05. For all tests, a P value of less than 0.05 will be considered statistically significant.

Pain is a subjective measure. We will be using an analog pain scale and reference them to the patients pre and postoperatively to account for this. Patients may take over the counter pain medication postoperatively. We cannot control the patient's use of over the counter pain medications while at home, thus we will have to rely on their accuracy and honesty for this study.

Patients will be called daily to ensure completion of daily log books. If they are not able to do this, they will be removed from the study analysis. If the patients return to clinic at 4-6 weeks post-surgery and they have completed their logs, their data will still be accepted. But if there is missing data, they will be removed from the analysis.

11 Source Documents and Access to Source Data/Documents

All data will be stored on HIPAA compliant and encrypted REDCap, approved by the institution and managed by MCIT.

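### Ten patients per arm is said to suffice for detecting any difference; at that size the planned pain and PACU-time tests reach 80% power only for very large effects

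*Combined protocol and SAP*

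**What the plan says.** Section 10.1.1 (General Approach) says the trial is powered from a previous similar study at the institution, and concludes "we will need 10 patients for each individual treatment arm to detect any difference in the outcome". This is the only justification of the size. The Protocol Summary and sections 5.4 and 5.6 repeat the numbers without a calculation.

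Section 2.2.1 describes the earlier study by direction only: "Patients in that study who received thrombin and local anesthetic before wound closure had lower pain levels", compared with local anesthetic alone. The new hypothesis in the same section is a further improvement "in the groups with a tranexamic acid + thrombin + local anesthetic than the groups with just thrombin + local anesthetic". Section 3.1 makes this part of the primary objective: "We want to determine the efficacy of this treatment over treatment with thrombin and local anesthetics and just local anesthetics alone".

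Section 10.1.2 plans to analyze pain with "a series of two proportion z tests with a family error rate equal to 0.05", and PACU time with "a one way analysis of variance test followed by a Tukey-Kramer post hoc test will be performed". It names no cutoff, day or number of tests for pain.

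On numbers and allocation, section 10.1.1 says "Simple randomization will be used to determine the treatment arm" and sets minimums of 10 per arm and 40 in total. Section 5.4 recruits until each group has 10, for a total of 40. Section 5.6 says "It is expected that approximately 40 participants will be enrolled in order to produce 40 evaluable participants", while section 10.1.2 removes patients with missing log data from the analysis.

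**The concern.** A sample size gives a certain power against a stated effect, with a stated variability and error rate. The sentence in section 10.1.1 states none of these and claims sensitivity to every effect. Its cited basis concerns arm 2 against arm 1, whereas the new question is what an antifibrinolytic adds to thrombin, that is, arms 3 and 4 against arm 2. Nothing in the document sizes that increment.

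At stake is how a null result is read. An IRB member or reader told that 10 per arm can see any difference could take a non-significant antifibrinolytic comparison as evidence of no effect, when the trial would often miss even a large one.

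**Working it through.** **The plan's own figure.** The 10 cannot be reproduced, because no effect, SD, rate, power or sidedness is given. The calculation can only be inverted at n = 10.

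**Inputs.** From the document: 10 per arm, four arms, 0.05 family rate, two-proportion z tests for pain, ANOVA with Tukey-Kramer for PACU time. Assumed: two-sided tests, 80% power, exactly 10 evaluable per arm, Bonferroni splitting, pain response rates symmetric about 50%. Four comparisons means two antifibrinolytic arms against two comparators; six means all pairs at one time point.

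**PACU time.**
- Normal approximation, unadjusted: d = (1.960 + 0.842) × √(2/10) = 1.25 SD.
- Noncentral t with noncentrality d√(10/2), unadjusted: d = 1.32 SD on 18 df and 1.29 SD on 36 df, so about 1.3 SD.
- Tukey-Kramer, four groups, 36 df: q = 3.809, critical t = 3.809/√2 = 2.693, giving d = 1.59 SD.

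**Pain.** With x1 and x2 responders, z = |x1 − x2|/10 ÷ √(2p(1 − p)/10), where p = (x1 + x2)/20. The critical values are 1.960 (0.05), 2.498 (0.05/4) and 2.638 (0.05/6).
- Observed 3/10 versus 7/10: z = 0.4/√0.05 = 1.79, not significant even at 0.05.
- Observed 3/10 versus 8/10: z = 0.5/√0.0495 = 2.25, significant at 0.05 but not after splitting.
- Observed 3/10 versus 9/10: z = 0.6/√0.048 = 2.74, significant at all three levels.

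Exact power is the sum of Bin(x1; 10, p1) × Bin(x2; 10, p2) over all significant outcomes. The last column is the largest exact type I error over all common response rates.

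| Pooled z test at | 80% power needs | Power, 30% vs 70% | Power, 20% vs 80% | Max. type I error |
|---|---|---|---|---|
| 0.05 | 20% vs 80% | 42% | 80% | 0.042 |
| 0.05/4 = 0.0125 | 16% vs 84% | 24% | 63% | 0.013 |
| 0.05/6 = 0.0083 | 16% vs 84% | 24% | 63% | 0.012 |

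The rows for 0.05/4 and 0.05/6 nearly coincide because the set of significant outcomes hardly changes. At 0.05/6 the test runs somewhat above its nominal level, so that row is mildly favourable; the normal approximation gives about 14% versus 86%, and so does a cutoff raised until the exact error is below 0.0083.

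Other variants exceed their level by more. Maximum exact type I error is 0.041 for the pooled test at 0.025. For the unpooled test it is 0.095 at 0.05, 0.042 at 0.05/4 and 0.023 at 0.05/6. Detectable differences from those tests look better only because the tests reject too often.

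**Arm sizes.**
- If recruitment stops at 40, the probability of exactly 10 in every arm is 40!/(10!⁴ × 4⁴⁰) = 0.0039. The smallest arm has 7 or fewer with probability 0.64, and its median is 7.
- If simple randomization continues until every arm has 10, simulation gives a median total of about 52 (5th to 95th percentile 43 to 69).

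**The case against.** The best defence is that the wording is loose but the number may be sound. An earlier study is cited, and if it showed an effect of about 1.3 SD, 10 per arm would give 80% power for one unadjusted comparison. That stands as far as it goes. A reader might infer that 10 is an arithmetic error or that the trial is wrongly sized; the document does not support that, because the earlier study's figures are not in it. The defence does not rescue a claim to detect any difference, nor carry over to the antifibrinolytic comparisons or the multiplicity-adjusted tests.

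A reader might also infer that arms will certainly fall below 10 through simple randomization. That holds only if recruitment stops at 40. Sections 5.4 and 10.1.1 can be read as recruiting to at least 10 per arm, in which case the total grows instead. What stands is that the three statements cannot in general all hold, and that section 5.6 leaves no allowance for patients removed under section 10.1.2.

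Nor does the document say that a non-significant result will be taken as no effect; that is a risk the sentence creates, not a stated plan. Finally, the pain figures rest on an endpoint whose dichotomy is undefined. That limits their precision, but at the levels tabulated every PACU-time or pain figure is very large, and separate daily tests would lower power further.

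**Conclusion.** The concern holds as a fault in the power statement. The claim in section 10.1.1 is one no finite sample can meet, and no other section supplies inputs that would turn it into a valid one. Under the assumptions listed, 80% power at 10 per arm requires about 1.6 SD for PACU time with Tukey-Kramer (1.3 SD unadjusted). For pain it requires about 20% versus 80% for a single comparison at 0.05, and about 16% versus 84% over four or six comparisons (nearer 14% versus 86% for six if the level is strictly held). A true 40-point pain difference, 30% versus 70%, would be missed about 58% of the time at 0.05 and about 76% after splitting. No figure is offered for pill count. The fixed-n figures do not depend on how the arm-size conflict is resolved; fewer evaluable patients per arm would make the PACU-time figures worse (at 8 per arm, Tukey-Kramer needs 1.80 SD).

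**What to change.** With the planned enrolment unchanged, remove the closing clause of the sentence in section 10.1.1 that promises detection, and write:

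> Ten patients per arm is based on an earlier study of thrombin plus local anesthetic versus local anesthetic alone [state the effect, SD and power used]; it was not sized for the antifibrinolytic comparisons. With 10 evaluable patients per arm, two-sided tests and 80% power, the detectable difference is about 1.6 SD for PACU time (Tukey-Kramer) and, for pain (pooled z test, rates symmetric about 50%), about 16% versus 84% with the family error rate split over four or six comparisons (20% versus 80% for a single comparison at 0.05). Smaller effects will not be reliably detected, and a non-significant comparison will not be interpreted as no difference.

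Recompute the pain figure once the dichotomy, day and number of comparisons are defined; for six comparisons, consider the stricter 14% versus 86%. Do not substitute the pooled 0.025 figure or any unpooled figure, because those tests exceed their nominal level by a wide margin at this size.

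Separately, reconcile simple randomization and the minimum of 10 per arm (sections 5.4 and 10.1.1) with the total of about 40 (Protocol Summary, sections 5.4 and 5.6). Say whether recruitment stops at 40 or continues until every arm has 10. State also that removing patients with missing log data can leave fewer than 10 evaluable per arm.

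The rewording needs no added patients or data. Its cost is a less favourable sensitivity statement, plus the decisions on the pain dichotomy and comparison family needed to finalize the pain figure. Resolving the arm-size conflict could change the total if the sponsor chooses to continue until every arm has 10.

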10.1.2 Analysis of the Primary Efficacy Endpoint(s)

Data will be expressed either as a mean (SD) or median and interquartile range (IQR). To evaluate PACU time as a function of each group, a one way analysis of variance test followed by a Tukey-Kramer post hoc test will be performed. To assess the number of pain pills need as a function of each group, a Kruskal-Wallis test followed by a Dunn post hoc analysis will be performed. To compare pain levels between the treatment arms, pain scores on a scale of 1 (lowest aka no pain) to 10 (highest pain experienced in life) will be collected daily via a patient log. They will be analyzed as a change from baseline (preoperative) pain levels and analyzed used a series of two proportion z tests with a family error rate equal to 0.05. For all tests, a P value of less than 0.05 will be considered statistically significant.

Pain is a subjective measure. We will be using an analog pain scale and reference them to the patients pre and postoperatively to account for this. Patients may take over the counter pain medication postoperatively. We cannot control the patient's use of over the counter pain medications while at home, thus we will have to rely on their accuracy and honesty for this study.

Patients will be called daily to ensure completion of daily log books. If they are not able to do this, they will be removed from the study analysis. If the patients return to clinic at 4-6 weeks post-surgery and they have completed their logs, their data will still be accepted. But if there is missing data, they will be removed from the analysis.

11 Source Documents and Access to Source Data/Documents

All data will be stored on HIPAA compliant and encrypted REDCap, approved by the institution and managed by MCIT.

Source data is all information, original records of clinical findings, observations, or other activities in a clinical trial necessary for the reconstruction and evaluation of the trial. Source data are contained in source documents. Examples of these original documents, and data records include: hospital records, clinical and office charts, laboratory notes, memoranda, subjects' diaries or evaluation checklists, pharmacy dispensing records, recorded data from automated instruments, copies or transcriptions certified after verification as being accurate and complete, microfiches, photographic negatives, microfilm or magnetic media, x-rays, subject files, and records kept at the pharmacy, at the laboratories, and at medico-technical departments involved in the clinical trial. It is acceptable to use CRFs as source

CONFIDENTIAL

This material is the property of the NYU School of Medicine and Langone Medical Center. Do not disclose or use except as authorized in writing by the study sponsor
Interventional Template Version: 11 January 2019

documents. If this is the case, it should be stated in this section what data will be collected on CRFs and what data will be collected from other sources.

The study case report form (CRF) is the primary data collection instrument for the study. All data requested on the CRF must be recorded. All missing data must be explained. If a space on the CRF is left blank because the procedure was not done or the question was not asked, write "N/D". If the item is not applicable to the individual case, write "N/A". All entries should be printed legibly in black ink. If any entry error has been made, to correct such an error, draw a single straight line through the incorrect entry and enter the correct data above it. All such changes must be initialed and dated. DO NOT ERASE OR WHITE OUT ERRORS. For clarification of illegible or uncertain entries, print the clarification above the item, then initial and date it.

Access to study records will be limited to IRB-approved members of the study team. The investigator will permit study-related monitoring, audits, and inspections by the IRB/EC, government regulatory bodies, and University compliance and quality assurance groups of all study related documents (e.g. source documents, regulatory documents, data collection instruments, study data etc.). The investigator will ensure the capability for inspections of applicable study-related facilities (e.g. pharmacy, diagnostic laboratory, etc.).

Participation as an investigator in this study implies acceptance of potential inspection by government regulatory authorities and applicable University compliance and quality assurance offices.

12 Quality Assurance and Quality Control

QC procedures will be implemented beginning with the data entry system and data QC checks that will be run on the database will be generated. Any missing data or data anomalies will be communicated to the site(s) for clarification/resolution.

Following written SOPs, the monitors will verify that the clinical trial is conducted and data are generated, documented (recorded), and reported in compliance with the protocol, GCP, and the applicable regulatory requirements (e.g., Good Laboratory Practices (GLP), Good Manufacturing Practices (GMP)).

The investigational site will provide direct access to all trial related sites, source data/documents, and reports for the purpose of monitoring and auditing, and inspection by local and regulatory authorities.

13 Ethics/Protection of Human Subjects

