4.2.2 Secondary Study Endpoints

Number of pain pills used

Total time in PACU

5 Study Enrollment and Withdrawal

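### PACU time from two hospitals is compared with no hospital term; adding one is a cheap gain in power, conditional on how far the hospitals differ

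*Combined protocol and SAP*

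**What the plan says.** Section 4.2.2 lists "Total time in PACU" as a secondary endpoint. Its whole analysis is in section 10.1.2, and the Statistical Analysis row of the Protocol Summary repeats it: "To evaluate PACU time as a function of each group, a one way analysis of variance test", with Tukey-Kramer comparisons afterwards. No covariate, transformation, distribution check or fallback is given for this endpoint. Pill count, in the same paragraph, gets a rank test.

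Section 5.6 states: "Patients will be recruited from NYU Langone Health and from Bellevue Hospital Center". Section 10.1.1 states: "Simple randomization will be used to determine the treatment arm". Hospital is not mentioned as a stratification factor.

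On size, section 10.1.1 says that "we will need 10 patients for each individual treatment arm to detect any difference in the outcome". It carries over no effect, SD or power from the earlier study that it cites.

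**The concern.** Time in a recovery unit may depend on local discharge routine as well as on the patient, so two hospitals may have different typical stays. An analysis by arm alone treats such a difference as unexplained noise. With about 10 patients per arm there is little information to spare, and section 2.2.1 expects shorter PACU stays with tranexamic acid added to thrombin and local anaesthetic. A real reduction could be missed because of variation that the trial can identify, since hospital is known for every patient without collecting anything new.

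**Working it through.** **The plan's own figure.** Ten per arm cannot be reproduced, because no effect, SD or power is stated. Solving backwards for one pairwise comparison (two-sided 0.05, 80% power): (1.96 + 0.84) × √(2/10) = 1.25 SD. Only large differences are detectable, before any allowance for multiple comparisons.

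**Effect of leaving hospital out.** Let p be the share of patients at one hospital, δ the difference in mean stay and σ the within-hospital SD. The unadjusted analysis has error variance of about σ² + p(1 − p)δ². The hospital term removes the second part.

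**Symmetric minutes.** Assumed, not from the documents: arm means 100, 85, 70 and 70 minutes, σ = 25, p = 0.5, 10 per arm.
- Grand mean 81.25. Squared deviations: 351.56 + 14.06 + 126.56 + 126.56 = 618.75. Times 10 patients per arm = 6187.5.
- Noncentrality λ = 6187.5 / error variance. Power comes from the noncentral F with 3 and 36 degrees of freedom.

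| δ (min) | Error variance | λ | Power, one-way ANOVA: formula (simulated) | Simulated power with hospital term |
|---|---|---|---|---|
| 0 | 625 | 9.90 | 70% (70%) | 69% |
| 15 | 625 + 56.25 = 681.25 | 9.08 | 66% (67%) | 69% |
| 30 | 625 + 225 = 850 | 7.28 | 56% (56%) | 69% |
| 45 | 625 + 506.25 = 1131.25 | 5.47 | 43% (43%) | 69% |

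Formula and simulation agree. The hospital term costs 1 to 2 points at δ = 0 and gains about 26 at δ = 45.

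**Right-skewed minutes.** Assumed log-normal, 50:50 split, raw-scale analysis without and then with the hospital term; simulation error is 1 to 2 points.
- 10 per arm, arms 3 and 4 at 0.55 times arms 1 and 2, 2.2-fold hospital difference: 41% to 52% at log SD 0.6, and 70% to 91% at log SD 0.4.
- Simple randomisation, log SD 0.5, time ratio 0.6 in the strongest arms: 50.4% to 49.0% with no hospital difference, 45.8% to 47.7% at 1.5-fold, 31.3% to 44.9% at 2.0-fold.

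Over log SD 0.4 to 0.6 the change is about -2 to 0 points with no difference, 1 to 8 at 1.5-fold and 9 to 26 at 2.2-fold.

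**These bands are not bounds.** With a weaker effect (ratio 0.7, log SD 0.5) a 2.0-fold difference gave only 16.4% to 22.2%. With less spread (ratio 0.7, log SD 0.3) a 1.5-fold difference already gave 47.6% to 64.4%.

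**Unequal split.** At δ = 45 the unadjusted error SD is √1131.25 = 33.6 for p = 0.5, √(625 + 0.16 × 2025) = 30.8 for p = 0.2, and √(625 + 0.09 × 2025) = 28.4 for p = 0.1. The benefit shrinks as one hospital dominates.

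**Type I error.** In log-normal runs with a hospital effect, the planned ANOVA rejected a true null in 3.8% to 5.1% of trials.

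**Scale.** With symmetric minutes, log plus hospital had 59% to 60% power against 69% for raw plus hospital. With log-normal minutes (ratio 0.6, log SD 0.5, 2.0-fold) logs raised power from 44.9% to 53.7%.

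**The case against.** The strongest reply is that the plan contains no error here. A one-way ANOVA after randomisation is valid, the endpoint is secondary, and every input to the power figures is assumed. That stands: this is an improvement, not a correction.

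Three stronger readings are tempting, and the documents support none of them.

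- A reader might infer that hospital imbalance biases the comparison. With a 50:50 split, two arms of 10 differ by 4 or more patients from one hospital in 2 × 60460 / 2²⁰ = 11.5% of allocations, and the largest gap among four arms reaches 4 in about 39%. But chance imbalance under randomisation is already part of the test's error rate, which stays near 5%.
- A reader might infer that the plan forfeits a definite 10 to 30 points of power, recoverable by a log-scale model with a hospital term. Across 180 assumed log-normal scenarios that model gained from 0 to 45 points, and 93 scenarios gained fewer than 10.
- A reader might infer that logs are required because durations are usually skewed. The documents do not describe the distribution, and logs cost about 10 points if minutes are symmetric.

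Nor does the point extend to the other endpoints. Section 10.1.2 plans two-proportion z tests for pain, so there is no pain model to which a hospital term could be added, and nothing here supports changing the pill-count test.

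**Conclusion.** The point holds as a low-cost gain in efficiency for one secondary endpoint. The planned PACU analysis leaves any hospital difference in the error term, and the trial is small enough for that to matter if the hospitals differ materially. The size rests on an assumed 50:50 split and assumed distributions and effects: essentially nothing gained or lost if the hospitals are alike, a few points at 1.5-fold, and roughly 9 to 26 points at 2.2-fold or 45 minutes. It is smaller where the arm effect is weak or one hospital supplies most patients. Validity is not in question, and no single power loss can be attributed to this plan.

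**What to change.** In section 10.1.2, and in the Statistical Analysis row of the Protocol Summary, replace the one-way ANOVA for PACU time with a linear model in minutes that has arm (four levels) and hospital (two levels) as fixed effects. Test arm with the F test from that model. Apply the Tukey-Kramer comparisons to the hospital-adjusted arm means and report each difference with a 95% confidence interval.

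State the scale in the same sentence. Raw minutes is a reasonable default. If the team has grounds to expect right skew, it may choose logs and report ratios of geometric means, but the choice should be fixed before any PACU data are seen.

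Cost: SAP wording and one error degree of freedom (36 to 35), or about 0 to 2 points of power if the hospitals do not differ. No extra patients, visits or data are needed. The pain and pill-count analyses are unaffected.
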